2.2. Assignment of interventions

2.1.2. Allocation

- Randomization will take place after all baseline measurements have been completed.
- We will randomize patients in a 1:1.08 allocation ratio (Control:Intervention in Belgium (Flanders), Ireland, Italy, The Netherlands, and Portugal in a 1:1;45 allocation ratio in Poland. These are the most efficient allocation ratio's given the partially nested design (see sample size calculation).
- We will use permuted block randomisation with varying block sizes.
- Randomisation will be stratified by country.
- Randomisation lists will be uploaded in REDCap (Research Electronic Data Capture).⁴⁰ REDCap is a secure web-based software platform designed to support randomisation and data capture for research studies.

N.B. If, after the baseline measurements have been completed, a patient turns out not to be eligible for participation in the study after all, the patient will not be randomized and cannot take part in the study (s/he will be informed about this then).

2.1.3. Blinding

Due to the nature of the intervention which includes patients being visited by navigators, neither the older persons and their family caregivers nor the researchers/research assistants can be blinded to allocation. Data will be collected via questionnaires and interviews with a researcher or research assistant that is present for assistance and additional explanations. Those conducting the data analyses will remain blind as to what trial arm participants were randomized to.

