^{**} The Clinical Frailty Scale (CFS) will be used to determine whether the patient has declining or deteriorating health. More specifically, declining or deteriorating health means at least 1 change in CFS score ending in score 4 in the last 6 months, OR everyone scoring 5 or higher.

^{***} i.e. services whose main task is to provide palliative care (e.g. in Flanders, multidisciplinary palliative home care team, admission to palliative care unit).

families to help them accomplish that. Navigators are selected, trained, and mentored volunteers or professionals (licensed or unlicensed) (depending on the best fit with the health care context of the country or region of implementation). They have **face-to-face and/or telephone or IT-supported** contact with patients and family carers, every two weeks on average or in different intervals, as needed. Nav-Care has a clear and specific implementation model. Navigators are matched to patients and family carers by **navigator coordinators** who are also responsible for championing the intervention and for networking with and connecting to health and social care professionals in the community and in hospitals in the region. Navigators and coordinators are trained, coached, and mentored by a **navigation trainer** (someone from a nursing or other healthcare background and experience in palliative or supportive care) and trainings are competency-based and blended (14 hours of training at the start + monthly coaching sessions). The **Nav-Care Toolkit** (Table 3) supporting the implementation contains blended (part online, part in-person) training and implementation tools and manuals.

Nav-Care was designed to enhance, not replace, professional health and social care in the region where it is implemented and to be responsive to the individual needs and wishes of patients and families. While it has several defined core components, the intervention is highly adaptable, and should be tailored to individual patient and family needs and local contexts while retaining its core components and hence its functional integrity.

From Nav-Care© to NavCare-EU

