2.3. Data collection, management, and analysis

2.3.1 Data collection methods (for outcome and process evaluation)

Informed consent will be obtained either on a pen-and-paper form through in-person contact or by posting a form to the participant together with a post-stamped return envelope and asking them to mail it back to the research team (if in-person contact is not possible) (see Appendices 6 and 7 for information letters and informed consent documents). Participants who are neither able to meet the researcher in person, or send the informed consent form by mail will be given the option of informed consent by telephone, which will be audio recorded using encrypted devices with audio files stored securely, similar to procedures in an existing study that tested a range of remote options for enrollment and consent of older people into research studies. ⁵⁰ In case the participant is illiterate, the researcher will read the study information and consent form out loud to the participant. If they know how to sign, the participant will be asked to sign the informed consent form themselves, a witness will be asked to sign to confirm that the information has been read out loud to the participant and that he/she understood and agreed to take part.

After having obtained informed consent from both the older person and the close family caregiver (if present), the researcher/research assistant will perform baseline measurements. In case the first contact with the participants occurred by phone, the researcher/research assistant will make an appointment to meet with them in the older person's home (or other preferred location). After obtaining baseline measurements, the researcher will check to which intervention arm the older person (and family caregiver) is randomised (see 2.2.1) using RedCap and inform them to which group they are assigned. In case the older person and close family caregiver (if

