present) are randomised to the intervention group, the researcher/research assistant will inform them that they will be contacted by the navigator coordinator within one week. In case the patient and close family caregiver are randomised to the control group, the researcher/research assistant will tell them that they will be visited by the researcher after 12 weeks (approximately 3 months) and that they will be contacted by the navigator coordinator after 24 weeks (approximately 6 months). After each enrolment of a patient and family caregiver (if present), the researcher/research assistant will send the patient's contact details and group allocation to the navigator coordinator, who will then contact the patient and introduce the intervention at the appropriate time. As a visual aid, the researchers will give a leaflet to the participants with pictures of the different people involved in the study (i.e. researchers who will visit on a regular basis, intervention staff and names).

Data for primary, secondary, and tertiary or exploratory outcomes will be collected at baseline, at weeks 12, 24, 48 (and 72 in the control group) thereafter until the study end or until the patient's death (see figure under 2.1.6). For patients allocated to the intervention group, data collection will stop after 48 weeks; for those allocated to the control group, data collection will continue until 72 weeks after baseline. The researcher will try to perform the data collection with the patient (and their close family caregiver) within a timeframe of 1 week after each measurement time point.

Table 5 provides an overview of the measures used and information collected and the relevant time points for each throughout the study period. At each assessment point, the same measures will be administered, except for the collection of sociodemographic data that remain constant and that are collected at baseline only.

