Data collection will be through structured questionnaires during a face-to-face contact with the patient/family (at his/her preferred place). Questionnaires for patients will be administered by a researcher in a structured interview, and answers will be filled in by the researcher on a paper version of the questionnaire. Questionnaires for close family caregivers will be self-administered on paper (in the presence of the researcher if support is needed). Given that the questionnaire for close family caregiver contains questions that may be perceived as sensitive by the participants (e.g. on informal care burden), questionnaires for close family caregivers will preferably be administered in the absence of the older person with cancer (e.g. in a separate room).

If data collection during a face-to-face contact is not possible (e.g. because of COVID or other reasons) we will allow remote data collection as contingency (but not preferred) option, either through administration of the questionnaire through an online form or in a structured interview format through video call (e.g. Zoom). The mode of data collection will be determined by the researcher prior to each measurement in consultation with the patient and family caregiver. In case of remote data collection, some people may require support of a family carer or friend, and the researchers will encourage such support. The project consortium has ample experience in both face-to-face and remote (including online) data collection with older people in poor health, especially during the COVID-19 pandemic when this was the only way to obtain research data from patients. These methods were found to be acceptable and feasible and to provide high-quality data, given careful preparation of the data collection including identifying which participants needed support for remote data collection and ensuring they have it.

Each assessment will last around 45 minutes for patients and 30 minutes for family caregivers, but this will be tested during feasibility testing of measurements prior to the trial. This was shown to be an acceptable procedure and duration in previous trials with a similar population.⁵¹

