| Navigators | Short survey characteristics Individual | Visit reports | Short survey characteristics individual | CFIR: individual-characteristics |
| | | | (group) interview about experiences (barriers, facilitators, adaptations) | RE-AIM: implementation, maintenance |
| | | | | |
| Trainers | Diary about process / trainer after each training/mentoring session | Diary about process / trainer after each training/mentoring session | Group interview with all international trainers about experiences | RE-AIM: adoption, implementation maintenance |
| | | | | |
| Professionals involved in the recruitment and referral of patients | Involved in LAT for feasibility check intervention | Short survey every 2 months about recruitment | Interview /short survey about evaluation intervention characteristics and recruitment/referral | CFIR: innovation RE-AIM: reach, maintenance |
| | | | | |
| Patients/family | | questions about experiences in WP3 survey | Interview about experiences | RE-AIM: implementation |

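### Outcome interviewers are told the allocation by procedure, although they do not deliver NavCare-EU; this adds a reducible interviewer bias to the unavoidable bias of unblinded patients.

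*Combined protocol and SAP*

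**What the plan says.** The Blinding section (numbered 2.1.3, under 2.2) gives its reason first: "Due to the nature of the intervention which includes patients being visited by navigators". It concludes that "neither the older persons and their family caregivers nor the researchers/research assistants can be blinded to allocation". It adds that a researcher is present at data collection to assist and explain, and that only those analysing the data stay blind.

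Section 2.1.3 on the intervention assigns delivery to navigators, who are matched to patients by navigator coordinators. Researchers are not among those who deliver it.

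Section 2.3.1 sets out how the arm becomes known. After baseline, "the researcher will check to which intervention arm the older person (and family caregiver) is randomised (see 2.2.1) using RedCap and inform them". The researcher or assistant then sends the patient's "contact details and group allocation to the navigator coordinator". The researcher role returns for the follow-up visits. On mode of collection the section says: "Questionnaires for patients will be administered by a researcher in a structured interview, and answers will be filled in by the researcher". Caregivers complete their own forms. Online or video collection is allowed only as a contingency.

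Both primary outcomes are reported by the patient: 2 quality-of-life items and 19 social-support items (section 2.1.4, Table 5). Table 6 also lists, for patients and family during the intervention, "questions about experiences in WP3 survey".

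The SAP (Sensitivity analyses) limits the sensitivity analyses of the primary endpoints to missing-data assumptions. Under Interpretation, success requires p < 0.025 and a difference of at least 10 points on at least one primary endpoint.

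**The concern.** The stated reason and the conclusion do not match for one of the roles covered. Navigator visits tell the patient and the family which arm they are in. They do not by themselves tell the person who later asks the questions. The documented way that person learns the arm is a study procedure, and the procedure could be given to someone else.

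Baseline is completed before randomisation, so baseline interviews are unaffected. Follow-up interviews are not protected in the same way. A researcher who knows the arm and is there to explain items and write down answers may prompt, explain or record a little more favourably in one arm. Any such shift at week 24 enters the difference in change from baseline in full. Blind analysts cannot remove it, because it is already in the recorded score.

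**Working it through.** **Inputs** (protocol section 2.1.6; SAP Sample size and Interpretation): difference 10; SD 25; baseline correlation 0.3; two-sided alpha 2.5%; ICC 0.10 in the intervention arm only; 1.5 patients per navigator in five countries (5/6 of patients) and 10 in Poland (1/6); 115 control and 131 intervention patients evaluable; ratios 1:1.08 and 1:1.45.

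**Step 1: reproduce the plan's sample size.**
- Adjusted SD = 25 × √(1 − 0.3²) = 23.85. The normal formula gives 109 per arm. The t-based ANCOVA version gives 110 per arm, which is the stated 220 (power 80.2%).
- Variance factor in the intervention arm = 1 + m × ICC/(1 − ICC). This is 1.167 for m = 1.5 and 2.111 for m = 10. The square roots, 1.080 and 1.453, are the stated allocation ratios.
- Of 246 evaluable patients, the five countries contribute 205 (98.6 control, 106.4 intervention) and Poland 41 (16.7 and 24.3). The arms total 115.3 and 130.7.

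**Step 2: standard error.**
- Residual variance = 625 × 0.91 = 568.75.
- Five countries: 568.75 × (1/98.6 + 1.167/106.4) ≈ 12.0.
- Poland: 568.75 × (1/16.7 + 2.111/24.3) ≈ 83.5.
- Inverse-variance pooling: SE = √[1/(1/12.0 + 1/83.5)] ≈ 3.24. Power = Φ(10/3.24 − 2.241) = 80.1%, as planned.
- The smallest significant difference is 2.241 × 3.24 ≈ 7.3 points. The 10-point condition is therefore the binding part of the success rule.

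**Step 3: add an assumed interviewer bias b favouring NavCare-EU.**
- A: no true effect, significant in favour: P(Z > 2.241 − b/3.24).
- B: no true effect, full success rule met: P(Z > (10 − b)/3.24).
- C: true effect of 7 points, full success rule met: P(Z > (3 − b)/3.24).

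| b (points) | A | B | C |
|---|---|---|---|
| 0 | 1.25% | 0.1% | 18% |
| 1 | 2.7% | 0.3% | 27% |
| 2 | 5.2% | 0.7% | 38% |
| 3 | 9.4% | 1.5% | 50% |

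The values of b and the true effect of 7 are assumptions. The documents give neither. The SE is the planning value for global health/quality of life. No SD or correlation is given for the social-support scale, so the table cannot be carried over to that endpoint.

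**The case against.** The strongest counter-argument is that an interviewer in the home will often find out the arm anyway. A reader might infer that researchers know it only because they look it up, so that removing that step would give a blinded assessor. The documents do not support that. Patients know their arm and may say so. The survey includes experience questions (Table 6). Researchers record reasons for stopping the intervention in REDCap (section 2.3.1) and keep a log of communications with participants, including distress (section 2.4.2). In Belgium and the Netherlands, coordinators work with the researchers on training volunteers (section 2.1.1). The look-up is the certain route but not the sole one, so any masking will be partial.

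Second, both outcomes are reported by unblinded patients. Masking the interviewer leaves respondent bias untouched. This stands in full.

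Third, a reader might take 9.4% as the trial's false-success rate. It is not: under the SAP's joint rule the figure for this endpoint is 1.5%.

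Fourth, open-label conduct is declared in the protocol, the SAP and the registration record. Interviews are structured, data collectors are trained with role-plays, and analysts are blind. So this is a disclosed design choice and not a contradiction. The documents also name a role; they do not say that the same individual randomises and interviews a given patient.

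What survives is narrower. The reason given does not require the interviewing role to be told the arm, and interviewer bias is a separate source that can be reduced at little cost.

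**Conclusion.** The point holds as an avoidable weakness in procedure. The plan unblinds the role that interviews patients and records both primary outcomes, for a reason that applies to participants and does not require telling the interviewer. No planned sensitivity analysis addresses the result.

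The practical risk is mainly an intermediate true effect being lifted over the 10-point line: from 18% to between 27% and 50% at a true effect of 7, for an assumed bias of 1 to 3 points. With no true effect, the 10-point condition keeps full false success at 1.5% or less over the same range, although the p-value and confidence interval are still biased. These figures rest on the plan's own variance inputs, apply to global health/quality of life only, and illustrate a bias whose actual size is unknown.

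**What to change.** 1. In section 2.3.1, have the national trial manager, or another existing team member who does not interview that participant, open the allocation and inform the participant and the navigator coordinator. The alternative is needed because the documents do not say that trial managers are always separate from data collection. Through week 24, restrict the REDCap allocation field and the intervention-discontinuation entries from the outcome interviewer's user role.
2. Before the week-12 and week-24 interviews, ask participants not to mention whether they have a navigator. Record at each interview whether the arm became known.
3. Make sure the 21 primary items (2 + 19) come before any navigation-experience question, if the interview in Appendix 4 does not already do so. Its order cannot be seen in the text available.
4. Reword the Blinding section to say that outcome interviewers are not told the allocation through week 24 and that participants remain unblinded.

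Self-completion by patients at weeks 12 and 24 is not advisable. Baseline would still be by interview, so it would change the mode of administration within a change-from-baseline endpoint.

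Cost: protocol wording, REDCap user rights, and one disclosure call per participant moved to another existing role. No extra assessor is needed, and sample size, endpoints and care are unchanged. The limits are partial masking and respondent bias that remains.

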2.3. Data collection, management, and analysis

2.3.1 Data collection methods (for outcome and process evaluation)

Informed consent will be obtained either on a pen-and-paper form through in-person contact or by posting a form to the participant together with a post-stamped return envelope and asking them to mail it back to the research team (if in-person contact is not possible) (see Appendices 6 and 7 for information letters and informed consent documents). Participants who are neither able to meet the researcher in person, or send the informed consent form by mail will be given the option of informed consent by telephone, which will be audio recorded using encrypted devices with audio files stored securely, similar to procedures in an existing study that tested a range of remote options for enrollment and consent of older people into research studies. ⁵⁰ In case the participant is illiterate, the researcher will read the study information and consent form out loud to the participant. If they know how to sign, the participant will be asked to sign the informed consent form themselves, a witness will be asked to sign to confirm that the information has been read out loud to the participant and that he/she understood and agreed to take part.

After having obtained informed consent from both the older person and the close family caregiver (if present), the researcher/research assistant will perform baseline measurements. In case the first contact with the participants occurred by phone, the researcher/research assistant will make an appointment to meet with them in the older person's home (or other preferred location). After obtaining baseline measurements, the researcher will check to which intervention arm the older person (and family caregiver) is randomised (see 2.2.1) using RedCap and inform them to which group they are assigned. In case the older person and close family caregiver (if

present) are randomised to the intervention group, the researcher/research assistant will inform them that they will be contacted by the navigator coordinator within one week. In case the patient and close family caregiver are randomised to the control group, the researcher/research assistant will tell them that they will be visited by the researcher after 12 weeks (approximately 3 months) and that they will be contacted by the navigator coordinator after 24 weeks (approximately 6 months). After each enrolment of a patient and family caregiver (if present), the researcher/research assistant will send the patient's contact details and group allocation to the navigator coordinator, who will then contact the patient and introduce the intervention at the appropriate time. As a visual aid, the researchers will give a leaflet to the participants with pictures of the different people involved in the study (i.e. researchers who will visit on a regular basis, intervention staff and names).

Data for primary, secondary, and tertiary or exploratory outcomes will be collected at baseline, at weeks 12, 24, 48 (and 72 in the control group) thereafter until the study end or until the patient's death (see figure under 2.1.6). For patients allocated to the intervention group, data collection will stop after 48 weeks; for those allocated to the control group, data collection will continue until 72 weeks after baseline. The researcher will try to perform the data collection with the patient (and their close family caregiver) within a timeframe of 1 week after each measurement time point.

Table 5 provides an overview of the measures used and information collected and the relevant time points for each throughout the study period. At each assessment point, the same measures will be administered, except for the collection of sociodemographic data that remain constant and that are collected at baseline only.

Data collection will be through structured questionnaires during a face-to-face contact with the patient/family (at his/her preferred place). Questionnaires for patients will be administered by a researcher in a structured interview, and answers will be filled in by the researcher on a paper version of the questionnaire. Questionnaires for close family caregivers will be self-administered on paper (in the presence of the researcher if support is needed). Given that the questionnaire for close family caregiver contains questions that may be perceived as sensitive by the participants (e.g. on informal care burden), questionnaires for close family caregivers will preferably be administered in the absence of the older person with cancer (e.g. in a separate room).

If data collection during a face-to-face contact is not possible (e.g. because of COVID or other reasons) we will allow remote data collection as contingency (but not preferred) option, either through administration of the questionnaire through an online form or in a structured interview format through video call (e.g. Zoom). The mode of data collection will be determined by the researcher prior to each measurement in consultation with the patient and family caregiver. In case of remote data collection, some people may require support of a family carer or friend, and the researchers will encourage such support. The project consortium has ample experience in both face-to-face and remote (including online) data collection with older people in poor health, especially during the COVID-19 pandemic when this was the only way to obtain research data from patients. These methods were found to be acceptable and feasible and to provide high-quality data, given careful preparation of the data collection including identifying which participants needed support for remote data collection and ensuring they have it.

Each assessment will last around 45 minutes for patients and 30 minutes for family caregivers, but this will be tested during feasibility testing of measurements prior to the trial. This was shown to be an acceptable procedure and duration in previous trials with a similar population.⁵¹

After participants complete the questionnaire/structured interview, the researcher will enter the de-identified responses into REDCap. REDCap is software for building and managing questionnaires and facilitating electronic data collection and storage. This database is accessed on a secure network server that is password protected.

Participants may withdraw from the data collection or voluntarily stop intervention sessions (e.g. because it is experienced as too burdensome, the patient is too busy, or too ill). The PI can also discontinue a participant from the study for the following reasons: due to an occurrence of an event, medical condition, or situation in which continued collection of study data would not be in the best interest of the client or the family caregiver. In case participants only wish to withdraw from the data collection, they may still continue with the intervention (visits by navigator), if they wish so, and vice-versa. Reasons for discontinuing the data collection or intervention will be documented by the researcher/research assistant in REDCap, if participants wish to state them (they are not obliged to do so).

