Relevant concomitant care and interventions that are permitted or prohibited during the trial. There are no restrictions regarding concomitant care during the trial outside of the trial arms.

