2.1.7. Recruitment

Pragmatic trials typically aim to recruit broader groups of patients from a variety of settings to represent all who may benefit from the intervention should it be implemented in standard care. ²⁸ Hence, we will recruit participants from a range of settings where patients from the target population receive care/support (i.e. hospitals, community or volunteer organisations).

Each country has a recruitment strategy in place, aimed to achieve enrolment of the targeted sample size into the pragmatic RCT (see sample size calculation in section 2.1.6) and aiming to recruit a diverse the sample in terms of age, gender, cancer diagnoses, cancer care regime (curative or non-curative/no treatment), education as proxy for socio-economic status (higher vocational training or university versus lower education), and living situation as proxy for aspects of social vulnerability (eg. also participants living alone).

Recruitment will run over 12 months or until the targeted sample size is achieved.

Recruitment strategies to obtain these recruitment objectives involve the following:

- **Establishing close partnerships** with local stakeholders such as hospitals or community organizations within the region where the intervention is rolled out. These partnerships have partly already been set up and will be further developed throughout the trial period as part of the key tasks of the navigator coordinator. Specifically with regard to Ethics approvals, recruitment via hospitals will usually need an additional ethical approval by the local Ethical Committees, which researchers will ensure to obtain next to obtaining approval from their own central Ethical Committees.

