- Pragmatic fast-track randomized controlled trial
- Superiority
- Parallel-group
- 1:1.08 allocation ratio (Control:Intervention) in Belgium (Flanders), Ireland, Italy, the Netherlands, and Portugal
- 1:1.45 allocation ratio (Control:Intervention) in Poland
- Non-blinded
- Partially nested design until week 24: patients in the intervention group are clustered within navigators, but patients in the control group are not (for the analysis of primary outcomes)
- Fully nested design from week 24 onwards

Interventions

Intervention = the NavCare-EU intervention plus care as usual

Patients allocated to the intervention group will immediately receive the NavCare-EU intervention plus care as usual for 48 weeks (12 months). The NavCare-EU intervention is a face-to-face and tele-

supported non-pharmacological intervention. The central component is a patient navigator, a dedicated person with or without a health-related background who engages with patients on an individual basis.

Navigators collaborate with patients and family caregivers throughout the continuum of supportive, palliative, and end-of-life care. Their main activities focus on addressing the needs, quality of life, and wellbeing of patients and family caregivers, the provision of information and psychosocial support, and ensuring people can connect to and access necessary services or resources. Every two weeks, navigators have face-to-face and/or telephone or IT-supported contact with patients and family carers, or in different intervals, as needed.

In the case of volunteers as navigator, expected caseload is one or two patients per navigator; in the case of professionals, a higher caseload per navigator is possible. The mean number of patients per navigator is expected to be 1.5 in Belgium (Flanders), Ireland, Italy, the Netherlands, and Portugal, and 10 patients in Poland.

Navigators are matched to patients and family carers by navigator coordinators. Navigators and coordinators are trained, coached, and mentored by a navigation trainer.

International trainers will aid country trainers to implement the intervention in their specific healthcare contexts and address country-generic and country-specific barriers and facilitators.

Control = care as usual

Patients allocated to the control group will first receive care as usual for six months (24 weeks) followed by the NavCare-EU intervention plus care as usual for 12 months (48 weeks).

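### Control patients' names and allocation go to the navigator coordinator at enrolment, about 24 weeks before any planned contact: an avoidable contamination risk

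*Combined protocol and SAP*

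**What the plan says.** Protocol 2.3.1 describes one hand-over step and does not separate the arms. Following every enrolment the researcher passes on "contact details and group allocation to the navigator coordinator, who will then contact the patient and introduce the intervention at the appropriate time". The preceding sentences define that time. Intervention patients are told that "they will be contacted by the navigator coordinator within one week"; controls are told "that they will be contacted by the navigator coordinator after 24 weeks (approximately 6 months". The SAP (Interventions, control) agrees: controls "first receive care as usual for six months (24 weeks) followed by the NavCare-EU intervention".

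Protocol 2.1.3 describes coordinators as the people who match navigators to patients and "who are also responsible for championing the intervention and for networking with and connecting to health and social care professionals". Section 2.1.7 describes building partnerships with local hospitals and community organisations "as part of the key tasks of the navigator coordinator". On concomitant care, 2.1.3 states: "There are no restrictions regarding concomitant care during the trial outside of the trial arms".

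The bereavement procedure in 2.1.3 (criteria for discontinuing or modifying allocated interventions) has the navigator telephone the bereaved participant and is not limited by arm.

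**The concern.** The hand-over must be prompt, because the same step serves intervention patients who are due a call within a week. The coordinator therefore holds an identified, allocation-labelled list of controls for essentially the whole 24-week comparison. Outcome visits are made by researchers, so they do not depend on this disclosure.

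The recipient matters. The intervention consists largely of connecting people to support, advocating and finding resources, in person or by telephone, and the coordinator works with the kind of organisations that refer and care for controls. An early call, a signpost to a service or a word to a treating team would resemble intervention content. Since concomitant care is unrestricted, it might not be recognised as a deviation. Under the intention-to-treat analysis, any such help to controls before week 24 would shrink the between-group difference. Social support, the second co-primary, includes informational and tangible support and is an obvious target of signposting.

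**Working it through.** **Hand-over against need**

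| | Intervention arm | Control arm |
|---|---|---|
| Details sent to coordinator (2.3.1) | after enrolment | after enrolment |
| First planned coordinator contact (2.3.1) | within 1 week | after 24 weeks |
| Gap | about 1 week | about 24 weeks |

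The protocol and SAP text contains no rule that withholds control identities until week 24, bars the coordinator from passing them on, or records navigation contact with controls before week 24.

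**Inputs** (Protocol 2.1.6; SAP, Sample size): difference 10 points; SD 25; baseline correlation 0.3; two-sided alpha 0.025; power 80%; ICC 0.10; 1.5 patients per navigator in five countries (5/6 of patients) and 10 in Poland (1/6); allocation 1:1.08 and 1:1.45; 115 + 131 = 246 evaluable patients.

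**Reproducing the plan**

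- Residual variance: 625 × (1 − 0.3²) = 568.75, SD 23.85.
- Balanced design: 2 × 568.75 × (2.241 + 0.842)² / 10² = 108.1, so 109 per arm, 218 in total. A noncentral-t calculation gives 220, as stated.
- Intervention-arm inflation, 1 + m × ICC/(1 − ICC): 1.167 for m = 1.5 and 2.111 for m = 10. The square roots, 1.080 and 1.453, match the stated allocation ratios.
- Combining the two strata by inverse variance requires 245.4 patients (115.0 control, 130.4 intervention), against 246 stated.

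**Standard error implied by 246 patients** (derived here; the plan prints none)

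- Outside Poland, 98.6 control and 106.4 intervention: 568.75 × (1/98.6 + 1.167/106.4) = 12.00.
- Poland, 16.7 and 24.3: 568.75 × (1/16.7 + 2.111/24.3) = 83.5.
- Combined variance: 1/(1/12.00 + 1/83.5) = 10.5, so SE = 3.24.

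**Effect of contamination.** Let a fraction c of controls receive a share s of the effect. The true difference becomes 10 × (1 − c × s), and power = Φ(difference/3.24 − 2.241). Both c and s are assumptions; the documents give neither.

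| c | s | Difference | Power |
|---|---|---|---|
| 0 | – | 10 | 80.1% |
| 5% | 1/4 | 9.875 | 79.0% |
| 10% | 1/4 | 9.75 | 77.9% |
| 5% | 1 | 9.5 | 75.5% |
| 10% | 1 | 9.0 | 70.4% |

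The SAP (Interpretation) also requires an estimated difference of at least 10 points. With a true difference of 10 the chance of that is 0.50; with 9.0 it is 1 − Φ(1.0/3.24) = 0.38.

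These figures cover global health status/quality of life only. The plan has no power calculation for social support.

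**The case against.** The plan already fixes when controls are contacted, so contamination requires someone to depart from a stated rule, and the documents report no rate or incident. This stands: the point is a risk, not an error in the design.

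A reader might infer that early contact would go undetected. The documents do not support that. Coordinators keep diaries and navigators report each client visit (2.3.2), service use is collected at weeks 12 and 24 (Table 5), independent monitors review protocol compliance (2.4.3), and the SAP's CONSORT diagram counts patients who did not receive their allocated intervention. What remains is that none of these is specified as a check on navigation reaching controls. The Quality Assurance Manual and Appendices 9 and 14 were not available here and may contain further rules.

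A reader might also infer that the coordinator has no use at all for control identities before week 24. That goes too far. The bereavement procedure allows the coordinator to notify the national trial manager of a death, and has a navigator make the call, in either arm.

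Full-effect contamination is an upper-end scenario. NavCare-EU is a matched navigator with contact about every two weeks; a single tip is much less. The quarter-effect rows are the fairer guide to casual leakage, and there the loss is one to two percentage points of power.

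Finally, withholding the list does not close every route. Coordinators may know some controls through recruitment partnerships, and all participants receive a leaflet picturing intervention staff. That limits the benefit of the change but does not justify handing over the list.

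**Conclusion.** The point holds as an avoidable risk. The protocol gives the coordinator the identities and allocation of controls about 24 weeks before the only scheduled contact with them, and the contact time is the sole stated barrier. Any leakage would bias towards no difference.

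The size cannot be known from the documents. For global health status/quality of life, power would fall from 80% to about 79% or 78% if 5% or 10% of controls received a quarter of the effect, and to about 76% or 70% if they received all of it. These figures rest on the plan's own design values, a derived SE of 3.24 and the assumed contamination rates. The documents do not show that contamination will occur. This is a low-cost improvement to trial conduct; sample size, endpoints and the delayed offer to controls are unaffected.

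**What to change.** In Protocol 2.3.1, limit the hand-over at enrolment to the intervention arm. For controls, the researcher sends contact details to the coordinator once the week-24 assessment is recorded as completed or definitively missed. A REDCap reminder can prompt this, with identities kept by the research team; the documents describe de-identified responses in REDCap and do not show it holding names for release to coordinators.

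Until then, give coordinators anonymous counts of controls with due dates so that they can plan navigator capacity. Add a log of any coordinator or navigator contact with a control before the week-24 assessment, and report it by arm.

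Reconcile the bereavement procedure in 2.1.3 with this rule, since it has a navigator telephone bereaved participants without regard to arm.

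The cost is a short amendment to 2.3.1, a reminder and a log. Coordinators would plan matching from counts rather than names, and some control identities may still reach them through referral networks.
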